### **12.1.21. Blood for Exploratory Analysis**

The peripheral blood immune phenotype will be assayed by whole blood flow cytometry.

Whole blood collected will be separated by magnetic bead cell separation in CD4, CD8, CD20 and CD14 fractions. Leukocyte fractions will be stored at  $\leq 68^{\circ}\text{C}$  for future epigenetic analysis. Additional whole blood collection and PBMC separation will be done for whole exome sequencing and RNA sequencing.

Blood will also be used for T-cell analysis for neoantigen and tetramer assays. Details of sample collection procedures are outlined in the Laboratory manual.

### **12.1.22. 30-Day Follow-up**

The final mandatory 30-Day Follow-Up Visit should be conducted at approximately day 30 after the last dose of study drug with the CT imaging visit or before the initiation of a new anti-cancer treatment, whichever comes first. All AEs that occur prior to the Follow-Up Visit should be recorded. Patients with an AE of Grade  $> 1$  will be followed until the resolution of the AE to Grade 0-1 or until the beginning of a new anti-neoplastic therapy, whichever occurs first.

Patients who discontinue trial procedures for a reason other than disease progression will move into survival follow up. Every effort should be made to collect information regarding disease status until the start of new anti-cancer therapy, disease progression, death, or end of study.

Information regarding post-study anti-cancer treatment will be collected if new treatment is initiated.

### **12.1.23. Unscheduled Visits**

If additional visits are needed (e.g., for resolution of an adverse event), the following procedures and evaluations may be performed as needed:

- Vital sign measurements (sitting blood pressure, heart rate, respiratory rate, temperature)
- Complete physical examination, including weight
- Hematology, serum chemistry and urinalysis
- Urine pregnancy test, if applicable. Positive results are to be confirmed with serum testing.
- Tumor assessment
- AE assessment
- Concomitant medications

## 13. STATISTICAL CONSIDERATIONS

### 13.1. General Design

This study will employ the standard “3+3” design for phase 1 clinical trials ([Storer 1989](#); [Simon 1997](#)) and as such no formal statistical analysis is planned for the escalation part of the study.

For the expansion cohort, the sample size calculation is based on a method proposed by Cancer Research UK for small oncology studies ([Khan 2012](#)). Based on data with atezolizumab in the unselected metastatic NSCLC population, the null hypothesis is set at an ORR of 20%, with the target ORR for the combination of 45%. With an  $\alpha=0.043$  and 80.29% power, at least 8 responses in 21 patients are needed to show success.

#### 13.1.1. Analysis populations

Safety Population: The safety population consists of all patients who receive at least one dose of the study medication. All safety and tolerability evaluations will be based on this analysis set.

PK/PD Population: The PK/PD population includes all patients without protocol deviations affecting interpretability of PK and/or PD.

Efficacy Population: primary efficacy analyses will utilize the treated population at the MTD, meaning all patients who receive at least 1 dose of study drug at the MTD; an additional analysis will include all treated patients, which is identical to the Safety Population.

#### 13.1.2. Interim analysis

One interim analysis is planned at the end of the escalation phase.

#### 13.1.3. General statistical considerations

The data will be presented in table formats listing the mean, standard deviation, median, range and number of patients per dose level for continuous data, or listing count and percentages for categorical data as appropriate.

#### 13.1.4. Primary objective: determine MTD based on proportion of patients with DLTs

The number and proportion (with 95% exact CI) of patients with DLTs is presented by dose for the escalation phase, the expansion phase and overall.

DLT will be categorized per the headings in the DLT section (hematologic, renal, viremia, clinical measles and other non-hematologic) and number and proportion (with 95% exact CI) of patients for each category is presented by dose for the escalation phase.

### 13.1.5. Overall safety analysis

The overall analysis of safety will be a comprehensive evaluation of AEs and/or toxicity, presented by dose and tumor type cohort and overall, based on:

- DLTs
- Recording of AEs by CTCAE V4.03
- Results of monitoring vital signs
- Results of clinical chemistry, hematology, coagulation, and urine analysis tests
- Changes in physical examination
- Occurrence of late or cumulative AEs
- Occurrence of autoimmune AEs
- Need for concomitant medications.

Results will be presented using descriptive statistics to display maximum toxicity grade for a given AE per patient by dose cohort, expansion cohort and overall.

Non-hematologic toxicities will be evaluated via the ordinal CTCAE standard toxicity grading only. Hematologic toxicity and other safety lab value changes will be assessed using continuous variables as the outcome measures (primarily nadir/peak and percent change from baseline values) as well as categorization via CTCAE standard toxicity grading. Overall toxicity incidence as well as toxicity profiles by dose level and patient will be explored and summarized. Frequency distributions, graphical techniques and other descriptive measures will form the basis of the analysis of these variables.

### 13.1.6. Secondary outcome measure/analyses

Efficacy: ORR and DOR will be calculated for the expansion cohort and overall using both RECIST 1.1 and irRECIST 1.1. Both efficacy endpoints will be summarized by descriptive statistics including confidence intervals. The distribution of ORR and DOR will be displayed graphically.

PFS is defined as the time from first dose of study drug until PD or death, whichever occurs first. PFS will be calculated for the expansion cohort and overall, using both RECIST and irRECIST, as above. Simple summary statistics will be supplemented by Kaplan-Meier survival estimates and related confidence intervals. Patients lost to follow-up or starting a new therapy without PD will be censored for time to event analyses at their most recent disease assessment.

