## 7. INVESTIGATIONAL PLAN

### 7.1. Overview of Study Design

This is a phase 1, dose escalation study of the combination of intra-tumoral MV-NIS and systemic atezolizumab in patients with recurrent and metastatic NSCLC. After the dose escalation phase of the trial, a dose expansion cohort will further investigate safety, clinical and immune responses at the MTD. [Figure 1](#) shows the study design. The study will involve 9-24 patients in the escalation phase and 15-18 in the expansion cohort, to provide a total cohort of 21 patients for efficacy evaluation at the MTD.

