## 8. STUDY POPULATION

### 8.1. Target Population

This study will be conducted in up to 24 patients with metastatic lung cancer, with histologic confirmation of the primary NSCLC histology and with at least one lesion amenable for intra-tumoral injection with MV-NIS.

Note: all eligibility criteria must be verified and submitted to the medical monitor to permit study registration. Day 1 may only occur after registration (at least 1 day and up to 7 days later).

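### The 8-of-21 response rule is correct for 21 patients at the MTD, but the protocol disagrees on which patients carry it, what happens above 21, and how many are enrolled

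*Combined protocol and SAP*

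**What the plan says.** **The rule.** Section 13.1 sets a null ORR of 20% and a target of 45%, with alpha 0.043. It continues: "80.29% power, at least 8 responses in 21 patients are needed to show success". The calculation is introduced with "For the expansion cohort, the sample size calculation is based on a method proposed by Cancer Research UK for small oncology studies".

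**Who the 21 are.** Section 7.1 plans "9-24 patients in the escalation phase and 15-18 in the expansion cohort", so that 21 patients at the MTD can be assessed for efficacy. Section 7.1.3 also gives 21 at the MTD. The 21 are therefore escalation and expansion patients at that dose, taken together.

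**The analysis sets.** Under Section 13.1.1, "primary efficacy analyses will utilize the treated population at the MTD", defined as everyone given at least one dose there. All treated patients form an additional analysis.

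**The analysis.** Section 13.1.6 states: "ORR and DOR will be calculated for the expansion cohort and overall using both RECIST 1.1 and irRECIST 1.1". PFS is handled in the same two groups. The summaries are descriptive with confidence intervals of unstated level and method, and the success rule is not repeated.

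**The total.** Section 8.1 states: "This study will be conducted in up to 24 patients with metastatic lung cancer".

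**Replacement.** Section 7.1.2 adds a patient for each one not evaluable for DLT. Section 8.5 allows replacement of patients who leave active treatment for reasons other than adverse events or progression.

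**The concern.** The 8-of-21 rule is the only numerical efficacy criterion in the trial, and its error rates depend on the denominator. Three parts of Section 13 point to different denominators: the expansion cohort (13.1), all patients treated at the MTD (13.1.1), and the expansion cohort plus everyone (13.1.6). An analyst working from the label in 13.1 and the groups in 13.1.6 could apply the cutoff to 15-18 patients.

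The MTD population itself need not be 21. A replaced patient who received one dose stays in it, and no cutoff is given for any other n.

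The enrolment figure in 8.1 does not fit the numbers in 7.1. If it were enforced as a total, the 21 might not be reached.

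**Working it through.** **Inputs.** p0 = 0.20, p1 = 0.45, cutoff 8, n = 21, alpha 0.043, power 80.29% (Section 13.1). Escalation 9-24, expansion 15-18, 21 at the MTD (7.1). Three patients per level, three more after a DLT (7.1.2).

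**Step 1: reproduce the plan.** With X binomial(n, p), P(X ≥ r) = 1 − Σ(x=0 to r−1) C(n,x) p^x (1−p)^(n−x).

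- p = 0.20, n = 21, r = 8: 1 − 0.95695 = 0.04305, the stated 0.043.
- p = 0.45, n = 21, r = 8: 1 − 0.19707 = 0.80293, the stated 80.29%.
- A cutoff of 7 would give 0.1085 at p = 0.20, so 8 is the smallest count with an upper tail of 0.05 or less.

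Section 13.1 does not state sidedness. The upper-tail calculation reproduces the figure. The nominal 0.05 is my assumption, since the plan gives only the attained 0.043.

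**Step 2: the same cutoff in the expansion cohort alone.**

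| n | P(X≥8) at 20% | P(X≥8) at 45% |
|---|---|---|
| 15 | 0.0042 | 0.347 |
| 16 | 0.0070 | 0.437 |
| 17 | 0.0109 | 0.526 |
| 18 | 0.0163 | 0.609 |

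**Step 3: more than 21 at the MTD.** Suppose six DLT-evaluable patients and one replaced patient are treated at the MTD in escalation, followed by the minimum expansion: 7 + 15 = 22.

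| n | cutoff 8: alpha / power | cutoff 9: alpha / power |
|---|---|---|
| 22 | 0.0561 / 0.848 | 0.0201 / 0.724 |
| 23 | 0.0715 / 0.885 | 0.0273 / 0.780 |

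The smallest count with upper tail ≤ 0.05 is 7 for n = 15-17, 8 for 18-21, 9 for 22-25 and 10 for 26-29.

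**Step 4: total enrolment.** The total is 21 plus the patients treated away from the MTD. Under the literal text of 7.1.2, a level fails only after filling to six. At least six patients are then away from the MTD: three at each of two lower levels if level 3 is the MTD, or six at a failed level otherwise. The minimum is 21 + 6 = 27, for example 3+3+3+18, 3+3+6+15, or 6 at the MTD + 6 at a failed level + 15. The upper end is 24 + 15 = 39, before replacements or a re-enrolled expansion cohort.

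If 24 were a cap on the whole study, at most 24 − 6 = 18 patients could be at the MTD, with power 60.9% (Step 2). If a failing level could stop at three, 24 − 3 = 21 would just fit (6+3+15).

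**Step 5: interval.** At 8/21 (38.1%) the Clopper-Pearson interval is 18.1-61.6% at 95% and 20.6-58.3% at 90%. The 90% lower limit exceeds 20% exactly when the one-sided tail is below 0.05, so it agrees with the rule.

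**The case against.** The strongest reply is that the plan already answers the main question. Section 13.1.1 names patients treated at the MTD as primary, 7.1 and 7.1.3 both give 21 at that dose, and the rule in 13.1 is written for 21. Section 13.1.6 is descriptive and does not move the cutoff. ORR is a secondary, preliminary endpoint in a phase 1 study whose primary objective is the MTD. The drift from 0.043 to 0.056 with one extra patient is small. All of this stands, and it limits the weight of the point.

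Four stronger readings are tempting, and the documents do not support them.

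- *That the stated alpha and power are wrong.* They are exact for 21 patients at the MTD.
- *That a cutoff of 8 will be applied to all treated patients*, where alpha would be 0.156 at n = 27 and 0.53 at n = 39. No section does this.
- *That the trial cannot reach its power because of a 24-patient limit.* The figure in 8.1 equals the escalation maximum in 7.1 and may be an escalation-only or leftover number. The 18-patient limit also needs failing levels to fill to six.
- *That the reported interval will contradict the rule.* That requires a 95% exact interval for ORR. Section 13.1.4 specifies one for DLT proportions only, and 13.1.6 gives no level.

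The reply does not remove the label in 13.1, the omission of the MTD population from 13.1.6, the absence of any rule for n other than 21, or the conflict between 8.1 and 7.1.

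**Conclusion.** The design calculation is right, but the text around it is inconsistent and should be corrected before response data are known.

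- **Analysis set.** Sections 13.1, 13.1.1 and 13.1.6 disagree. Reading the rule onto the expansion cohort, as the label in 13.1 invites, would cut power from 80.29% to 35-61%, with alpha 0.004-0.016.
- **Number at the MTD.** If replacement takes it to 22 or 23, a fixed cutoff of 8 has one-sided alpha 0.056 or 0.072. This assumes that replaced patients stay in the denominator, as the one-dose definition implies, and that expansion is not shortened to absorb them.
- **Study size.** Section 8.1 cannot be squared with 7.1, which implies 27-39 in total. Power of 61% follows only if 24 is a total cap and failing levels fill to six.

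The arithmetic is certain. What remains open is the sponsor's intent on the label in 13.1 and the figure in 8.1.

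**What to change.** 1. In 13.1, 13.1.6 and the matching synopsis text, name the Efficacy Population at the MTD (escalation plus expansion patients treated at that dose) as the primary set for ORR, DOR and PFS, and as the set carrying the success rule. Make all treated patients supportive. Remove the expansion-cohort label from the calculation.
2. State a one-sided exact binomial test of ORR ≤ 20% at 0.05, with the critical count set by the actual number treated at the MTD: 7 for 15-17, 8 for 18-21, 9 for 22-25, 10 for 26-29.
3. Show a two-sided 90% exact interval for ORR beside the test, so that the two agree.
4. Reconcile 8.1 with 7.1. Either give 27-39 in total plus any re-enrolled expansion cohort, or state that 24 refers to escalation only.

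These are wording changes with no new data collection. At n = 21 nothing changes. Holding alpha at 0.05 costs power just above that: 72% at n = 22 and 78% at n = 23, returning to 83% at n = 24.

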### 13.1.7. Pharmacokinetic and Pharmacodynamic analysis

Pharmacokinetic evaluation: results of SPECT/CT imaging to determine infected cells and kinetics of virus spread and elimination will be summarized by dose and time by descriptive statistics and displayed graphically.

Pharmacodynamic evaluation: tissue analysis for MV-NIS, tissue analysis for tumor micro environment and assessment of neoantigens and tumor specific immune response will be summarized by dose and time by descriptive statistics and displayed graphically.

### 13.1.8. Exploratory outcome measure/analyses (analysis will be detailed in the SAP)

Data will be gathered for a number of laboratory correlative variables for each patient. Descriptive statistics and simple scatter plots will form the basis of presentation of these data. Correlations between these laboratory values and other outcome measures will be carried out by standard parametric and nonparametric correlation procedures (Pearson's and Spearman's coefficients). Prerequisite normality testing of these data will be carried out via standard Shapiro-Wilk testing ([Shapiro and Wilk 1965](#)).

Where patterns of correlation are indicated, ordinary and partial correlation coefficients (controlling for dose levels) will be calculated. Inferential testing for significant shifts in the correlative laboratory data results across dose levels will be carried out only as a hypothesis-generating exercise. The small cell size will mean, for example, that only a shift of 1.5 standard deviations in the sample means can be detected via a one-sided Wilcoxon procedure with a 5% type I error rate. In all such situations, confidence intervals will be presented as the primary method of analysis. Hence, such hypothesis testing will only be used as exploratory for directing further research.

Ancillary timed endpoints/analysis: exploratory analysis may be carried out on time-related variables MV-NIS cohorts including time until any treatment related toxicity, time until treatment related grade 3+ toxicity and time until hematologic nadirs (WBC, ANC, platelets). Simple summary statistics will be supplemented by Kaplan-Meier survival estimates and related confidence intervals ([Pepe and Fleming 1991](#); [Lee 1992](#)). The effect of dose and ancillary dichotomized covariates such as age will be explored using log rank testing involving one covariate at a time. Again, the small sample size restricts the generalizability of such testing, but the results will provide preliminary indication for future research in subsequent phase 2 trials.

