### 6.3. Exploratory objectives

- To determine the time-course of viral infection, dissemination, and elimination through the measurement of NIS gene expression using SPECT/CT imaging.
- To assess viremia, viral replication, and viral shedding/persistence following intra-tumoral administration of MV-NIS and immunotherapy.
- To obtain preliminary data regarding the antitumor efficacy by serial measurements of radioiodine uptake by SPECT/CT, radiological ORR, DOR and PFS and to correlate with PD-L1 expression and other immune biomarkers.
- To characterize the peripheral blood immune phenotype, presence and peripheral blood repertoire representation of neoantigen-specific T cells, and cell-free DNA of patients at potential immunologic transition points including study enrollment, therapy initiation, during therapy, and at follow-up.
- To evaluate if therapy with MV-NIS, atezolizumab, or both alters the peripheral blood immune phenotype, presence and peripheral blood repertoire representation of neoantigen-specific T cells, or cell-free DNA.
- To characterize the tumor microenvironment by immunohistochemistry (IHC) for PD-L1 and other immune markers of interest on tissue prior to and at the completion of MV-NIS injection and following atezolizumab treatment.
- To evaluate if MV-NIS alter the pretreatment tumor microenvironment levels of PD-L1 or immune markers after therapy in the lesion injected with MV-NIS.
- To determine if lesions not injected with MV-NIS express comparable levels of PD-L1 or contain an immune marker milieu within the tumor microenvironment similar to the lesion injected with MV-NIS after treatment with MV-NIS and atezolizumab.

- To assess if changes to the circulating or tumor microenvironment immune biomarkers associate with clinical response.
- To evaluate the tumor genomic mutational burden by whole exome sequencing, level of neoantigen expression and signal transduction pathways by RNAseq prior to and after therapy with MV-NIS and atezolizumab.
- To determine if changes to the tumor genomic mutational burden, level of neoantigen expression or alterations in signal transduction pathways are associated with clinical response
- To assess the secondary efficacy parameters (ORR, DOR and PFS) using irRECIST in addition to classical RECIST 1.1.
- To compare PFS of the combination of MV-NIS and atezolizumab in patients with recurrent and metastatic NSCLC versus historical controls

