### **9.3.2. Additional Anti-Cancer Treatment and Radiotherapy**

Patients should not receive additional therapeutic anti-cancer treatment until after PD has been documented on study and follow-up study assessments have been completed. If a patient requires additional anti-cancer treatment without radiological evidence of PD, the date of new treatment start will be considered the date of PD. If a patient stops study drug (atezolizumab) without evidence of PD, the patient will enter the Follow-up Period and followed every 3 months until PD.

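### Biomarkers are to be related to PFS and DOR, which are censored, but the plan names only Pearson and Spearman coefficients; naming a censoring-aware method would recover power

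*Combined protocol and SAP*

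**What the plan says.** Among the exploratory objectives in Section 6.3 is to obtain "radiological ORR, DOR and PFS and to correlate with PD-L1 expression and other immune biomarkers". Section 13.1.8 gives the method for relating laboratory correlatives to outcomes: "Correlations between these laboratory values and other outcome measures will be carried out by standard parametric and nonparametric correlation procedures (Pearson's and Spearman's coefficients". It adds partial correlations controlling for dose level where a pattern has been indicated, makes confidence intervals the primary presentation, and labels the testing exploratory. Its heading defers detail to the SAP; the combined document contains no further detail.

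Section 13.1.6 treats PFS as a time-to-event outcome with Kaplan-Meier estimates. Patients lost to follow-up or starting new therapy without progression "will be censored for time to event analyses at their most recent disease assessment". Kaplan-Meier and log-rank also appear in 13.1.8, but for time to toxicity and time to haematological nadir, with dose and dichotomised covariates such as age. Neither they nor a Cox model is assigned to biomarkers against PFS or DOR.

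**The concern.** A correlation coefficient takes one number per patient. For a patient still progression-free at the data cut, that number is length of follow-up, not PFS. A Pearson or Spearman test on observed times therefore asks whether the biomarker is associated with the earlier of event and censoring. Two things could follow:

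- A real association is diluted, because a patient censored at two months ranks beside one who progressed at two months.
- A false association can appear if the biomarker is itself tied to length of follow-up. Dose levels open in sequence, so a dose-related biomarker in a pooled analysis could be.

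Section 13.1.8 says that this testing is meant to direct further research. Missed or misdirected signals would defeat that purpose. No dose decision or formal endpoint depends on it.

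**Working it through.** **1. The plan's own figure.** Section 13.1 states "80.29% power, at least 8 responses in 21 patients are needed to show success", with a 20% null, a 45% target and alpha 0.043. Exact binomial: P(X ≥ 8 | 21, 0.20) = 0.0431 and P(X ≥ 8 | 21, 0.45) = 0.8029. Both reproduce. They say nothing about the biomarker analyses, which carry no stated error rate or power; they supply n = 21.

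**2. What each method computes.** Let T be event time, C censoring time, Y = min(T, C), and δ = 1 if T ≤ C. Pearson and Spearman use (x, Y) and ignore δ. The Cox score test uses (x, Y, δ): U = Σ δᵢ(xᵢ − mean of x in the risk set at Yᵢ), V = Σ δᵢ(variance of x in that risk set), with U²/V referred to chi-square on 1 df.

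**3. Inputs.**
- From the documents: three patients per escalation level, three levels, 18 expansion patients with a 36-day pause after six, 21 at the MTD.
- Assumed, because the documents give no PFS median, accrual rate or data cut: exponential PFS with median m = 3, 6 or 12 months, accrual 1.5 per month, administrative censoring at last entry + 2, 6 or 12 months, a standard normal biomarker, two-sided 5% tests.

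**4. How much censoring this implies.** The first expansion patient enters 17/1.5 + 36/30.4 = 11.3 + 1.2 = 12.5 months before the last. At the +2 cut, expansion follow-up runs from 2 to 14.5 months; at +12, from 12 to 24.5. The chance of being event-free at C, at an average biomarker value, is 2^(−C/m):

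| m (months) | +2 cut: last / first expansion patient | +12 cut: last / first |
|---|---|---|
| 3 | 63% / 4% | 6% / <1% |
| 6 | 79% / 19% | 25% / 6% |
| 12 | 89% / 43% | 50% / 24% |

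**5. Power, 21 MTD patients, hazard ratio 2 per SD, +2 cut.** Ranges span repeat simulations of this design.

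| m (months) | Spearman | Cox score | Loss (points) |
|---|---|---|---|
| 3 | 50-53% | 66-70% | 15-17 |
| 6 | 36-38% | 56-58% | 19-20 |
| 12 | 22-23% | 43-45% | 20-23 |

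At the +12 cut the loss is 11-15 points for Spearman and 4-9 for Pearson. A different follow-up model (uniform over 1-19 months, m = 6, about 39% censored) gives Cox 60%, Pearson 42% and Spearman 40%. Over a wider set of assumptions at n = 21 the loss runs from about 5 to 33 points.

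**6. What share is censoring.** At m = 3 and the +12 cut, step 4 puts censoring at 6% or less for every expansion patient, yet Spearman still loses at least 11 points. That residual is mostly the lower efficiency of Spearman under proportional hazards. A little more reflects the Cox score test's own size (5-6.5% at n = 21). The widening to 15-23 points at the early cut is the part that tracks censoring.

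**7. Type I error, nominal 5%.**
- MTD set, one dose, biomarker unrelated to follow-up: 4-7% at all three medians and all three cuts.
- Nine escalation patients pooled, biomarker +1 SD per level and unrelated to PFS, m = 3 / 6 / 12. At +2: Spearman 8-9% / 14-16% / 24-25%, Pearson 7-9% / 15-17% / 24-27%, Cox 4-6%. Spearman at +6: 6.1% / 7.5% / 11.7%. At +12: 5.7% / 6.3% / 8.2%.
- All 27 pooled, Pearson: 7.1% / 12.3% / about 20% at +2, and 5.0% / 7.3% / 8.6% at +12. Spearman at +2 and m = 12: 11%.
- Partial correlation on dose, always applied: 3.7-6.7% in every pooled setting.

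As multiples of nominal, the +2 results run from 7/5 = 1.4 to 27/5 = 5.4.

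**8. DOR.** With eight responders and the 18.6-month median DOR from the appended label, the loss is about 3-11 points from a base of only 12-35%. No method does well at that size.

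**The case against.** The strongest reply is that the plan never says that censored times are entered as complete. Section 13.1.8 speaks of other outcome measures without naming PFS or DOR, defers detail, and elsewhere handles censoring correctly. This stands in part: complete-case entry is an inference. But 6.3 names DOR and PFS as outcomes to be correlated, and the only alternative for a plain coefficient is to drop censored patients, which discards data. Making confidence intervals primary does not help, since an interval for the same coefficient targets the same quantity.

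Three stronger readings are tempting, and the documents do not support them:

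- *That the tests generally reject at several times the nominal rate.* They do not in the MTD set, which Section 13.1.1 makes the primary efficacy population: with one dose, the dose route cannot operate. In pooled sets the planned dose-partial correlation removes the inflation. It is conditional on a pattern being seen, but a false marginal correlation would be such a pattern. The largest figures also need a 12-month median PFS. The appended label gives median overall survival of 12.6-13.8 months and median exposure of 3.7 months on atezolizumab alone, so the shorter medians are at least as relevant.
- *That the interim analysis will produce false biomarker findings.* Section 13.1.2 says only "One interim analysis is planned at the end of the escalation phase" and does not list biomarker correlations among its contents.
- *That the whole power gap is due to censoring.* Step 6 shows that it is not.

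ORR is binary and uncensored, so it lies outside this point.

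**Conclusion.** The concern holds as a minor one. An objective involving two censored outcomes is paired with coefficients that cannot accommodate censoring, and no censoring-aware method is assigned to it. If observed times are used as they stand, the main cost is power in the 21 MTD patients: about 15-23 points for Spearman at an early cut and 11-15 with 12 months of follow-up, under the assumed accrual, exponential PFS and hazard ratio of 2 per SD. This needs no confounding. Inflated type I error is a secondary risk, confined to pooled doses without dose adjustment, a dose-related biomarker, and an early, heavily censored cut. The near-5% result in the MTD set assumes that the biomarker is unrelated to entry date; nothing in the documents suggests otherwise. Exploratory status limits the severity, but the stated method is still the wrong tool for these two outcomes.

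**What to change.** In Section 13.1.8 or the SAP detail to which it defers:

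- Limit Pearson and Spearman to uncensored continuous outcomes.
- For PFS and DOR, use a Cox score test, or a censoring-aware concordance index, with the biomarker as a continuous covariate. Report the hazard ratio per SD with its confidence interval, in keeping with the plan's emphasis on intervals.
- Stratify by dose level whenever levels are pooled, rather than only after a pattern is seen.

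The cost is a few sentences and a few lines of code, with no extra data. The downside is that hazard ratios replace a single correlation coefficient.

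The same edit should settle which patients are censored. Section 13.1.6 censors those who start new therapy without progression, whereas Section 9.3.2 says that "the date of new treatment start will be considered the date of PD". The two must be reconciled before either analysis can be run.
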